9.7.2 Secondary Endpoints

For the FACT-G, leukemia-specific, FACIT –Fatigue and Geriatric Assessment Battery subscales, we will provide descriptive statistics and calculate Cronbach's alpha at each time point to assess reliability. Repeated measures analysis techniques will also be utilized to examine the treatment effect and time effect on FACT-Leu TOI score and FACIT Fatigue score. For patients randomized to the induction treatments, the longitudinal scores collected from time of randomization, two weeks after beginning induction therapy (at the time of nadir), and at 28 – 30 days after beginning induction therapy, will be analyzed according to the methods described in Schluchter⁵ and Schluchter, Greene and Beck⁶. These methods take into account the possibility of informative missingness by jointly modeling the longitudinal response (QOL scores) and the time to dropout.

We will also examine whether components of a comprehensive geriatric assessment or QOL scale could predict ability to complete AML treatment. For patients who received induction therapy, logistic regression models on whether patients complete induction treatment will be fitted with all those scores (FACT-Leu TOI, FACIT Fatigue, and each component of Geriatric Assessment Battery at time of induction randomization) as covariates and treatment effect as a factor. For patients who received consolidation therapy, logistic regression models on whether patients complete consolidation treatment will be

fitted with FACT-Leu TOI, and FACIT Fatigue scores at beginning of consolidation therapy as covariates and treatment effect as a factor. For patients who received decitabine maintenance therapy, logistic regression models on whether patients complete maintenance treatment will be fitted with FACT-Leu TOI and FACIT Fatigue scores at the time of maintenance randomization as covariates.

For those patients who go to allo transplant, the FACT-Leukemia and FACT Fatigue instruments will be administered at the following time points: at the beginning of the conditioning regimen and 100 days (\pm 14 days) post transplant. We will provide descriptive statistics of FACT-Leukemia and FACT Fatigue subscales at each time point. Paired t-tests will be used to examine the impact of allo transplant on FACT-Leu TOI and FACIT Fatigue.

9.8 Correlative Studies

The first goal of the correlative studies is to perform expression and methylation profiling on all patients receiving decitabine and to correlate their integrated epigenetic signatures with response to decitabine. The second goal is to examine the epigenetic profiles of remission marrow in patients randomized to observation vs. decitabine in E2906 to determine whether the epigenetic signature of apparently morphologically normal bone marrow is predictive of relapse or response to decitabine maintenance. These analyses will be exploratory in nature. Assume that 86 patients will receive decitabine maintenance treatment and 86 patients will be randomized to the observation arm. Among them, 45%-50% will submit samples and have sufficient material for expression and methylation profiling. Genomic microarrays will be used to study DNA methylation, and gene expression arrays will be used to study expression. Both types of arrays are made by the NimbleGen company. The assay for DNA methylation is HELP (HpaII tiny fragment enrichment by ligation-mediated PCR). DNA is digested in parallel with MspI (resistant to DNA methylation), and then the HpaII and MspI products are amplified by ligation-mediated PCR and hybridized using separate fluorochromes to a customized array. The analysis of HELP data involves quality analysis and normalization. The methods described in Thompson et.al (127) will be used to identify epigenetics signatures which are different between patients who relapsed and patients who did not relapse. Signatures identified by epigenetic analysis will be correlated with DFS using a LARS/LASSO approach (128,129) for each maintenance arm. For the gene expression data, we will use Dchip software to normalize the expression levels and generate model-based expression intensities. Genes will be filtered by examining ratios of standard deviation to the mean. Genes will be hierarchically clustered to find genes with high/low fold change/differences. Supervised analyses will be used to identify genes that are differentially expressed between patients who relapsed and patients who did not relapsed. Genes or epigenetic signatures identified by gene expression or epigenetic analysis will be correlated with DFS using LARS/LASSO approach (128,129).

A third goal is to study how genetic lesions cooperate to induce the resistant phenotype and to confer an adverse prognosis to elderly patients with AML. These analyses aim at elucidating in detail the spectrum of somatic alterations in elderly AML and at determining which alterations or pathways are the major

determinants of chemoresistance in this disease. While it is possible that thousands of coding and non-coding genes are affected by mutations or epigenetic lesions, these genes often have in common the perturbation of common pathways, such as DNA repair, RNA splicing, etc. This goal also aims at determining the biological functions perturbed by genetic lesions, using bio-assays and animal models. The E2906 patient cohort will allow a comparison between somatic mutations in leukemia oncogenes and tumor suppressor genes previously identified in younger AML patients accrued to E1900 with those dominating in elderly AML.

Rev. 2/12

We assume that 635 patients (87% of 727 patients) will submit samples and have sufficient material for mutation analysis. We estimate about 20 mutations will be examined. For a mutation with 50% prevalence, we assume for those mutated patients a 10% long-term cure rate and 7.5-month median overall survival in the non-cured group. With treatment arms combined, the study will have approximately 81% power to detect a 29% reduction in the hazard rate in wild-type patients, assuming 2 years of follow-up. The number of events needed is 528. For a mutation with 20% prevalence, we assume those mutated patients have a 10% long-term cure rate and 6.3-month median overall survival in the non-cured group. With treatment arms combined, the study will have approximately 81% power to detect a 35% reduction in the hazard rate in wild-type patients, assuming 2 years of follow-up. The number of events needed is 501. Those power calculations were based on a two-sided log rank test with the family-wise type I error rate controlled at 0.05 using the Bonferroni correction. For each mutation we will perform a stratified log-rank test (using the strata at randomization) adjusted for multiple testing using resampling and the min-p method of Westfall and Young (1993) as implemented in the R package multtest. In addition we will perform tests for interaction between treatment assignment and mutational status to identify potential predictive mutations. We will begin these analyses by assessing the prognostic relevance of known mutations on overall survival and response to therapy, including FLT3, DNMT3A, IDH1, IDH2, TET2, ASXL1, WT1, and MLL, and we will also include novel mutations identified in our discovery studies and by other efforts (including the AML TCGA project) to determine if novel mutations affect outcomes in this cohort of elderly patients with AML.

Rev. 2/12

We will also identify prognostic risk groups by using recursive partitioning and logistic regression, both of which are highly suitable for binary predictors. We plan to use a randomly chosen subsample of 423 (2/3 of 635) patients for training these models and the remaining 212 for validation.

Rev. 2/12

Another goal of the correlative studies is to explore the possible association of response to clofarabine with ABC-transporter P-glycoprotein (Pgp). We hypothesize that the relative expression of Pgp will determine differential activity of clofarabine in subsets of patients who overexpress Pgp, and will manifest itself in the CR rate. An aliquot of bone marrow or peripheral blood from pre-treatment samples will be evaluated for Pgp protein expression by flow cytometric assessment of binding of anti-Pgp antibody, MRK-16. In E3999, MRK-16 binding significantly correlated with P-glycoprotein function as a drug-efflux pump. We assume that 360 patients will receive clofarabine and 87% of those patients will submit samples and will have sufficient material for analysis. We assume about 20% of patients will overexpress Pgp and the CR rate of the patients who

overexpress Pgp is 30%. With 63 patients who overexpress Pgp the study will have 80% power to detect an effect size of 0.80 at the two-sided significance level of 0.05 using a Wilcoxon rank sum test. Effect size is defined as the difference of the expression of Pgp between CR patients and non-CR patients divided by the common standard deviation of the two groups. Table 4 presents the effect size to be detected with 80% power under various percentages of patients overexpress Pgp and various CR rates of those patients.

Table 4: Effect Size of the Expression of Pgp between CR Patients and non-CR Patients (two-sided $\alpha = 0.05$, power=80%)

CR rate of the patients who overexpress transporter	Percentages of patients overexpress transporter	Effect size to be detected
30%	40%	0.56
	30%	0.65
	20%	0.80
35%	40%	0.54
	30%	0.62
	20%	0.76

Rev. 2/12

In addition, expression of CXCR4, will be assessed in this study by flow cytometric assay to correlate the intensity of its expression with other established prognostic factors (in particular with cytogenetics) in patients receiving induction treatments. Expression intensity of CXCR4 will be divided into three groups (low, intermediate, high). Based on results of Spoo, et al ⁸⁷, it is anticipated that high/intermediate CXCR4 expression is associated with inferior clinical outcomes of response or survival. Therefore, the grading will be further simplified as high/intermediate vs. low. Data will be first analyzed by induction treatment arms. We assume 315 patients will receive induction therapy in each arm and have sufficient material for analysis, and among them, 35% of patients will have low expression of CXCR4⁸⁷. Assuming 40% overall CR rate in that treatment arm, there will be 85% power to detect a difference in CR rate if the CR rate in the low expression of CXCR4 group is 52% and 34% in the high/intermediate expression of CXCR4 group. Alternatively, assuming 45% overall CR rate in that treatment arm, there will be 81% power if the CR rate in the low expression of CXCR4 group is 56% and 39% in the high/intermediate expression of CXCR4 group. This power calculation is based on Fisher's exact test at two-sided significance level of 0.05. When data are available, logistic and Cox regression analysis, adjusted by treatment effect and prognostic factors (including cytogenetics), will be used to assess whether CXCR4 expression level is an independent predictor for response or survival.

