2.2 Secondary Objectives

2.2.1 To evaluate complete remission (CR) rates, duration of remission, and toxicity/treatment-related mortality of clofarabine in comparison with standard therapy (daunorubicin & cytarabine) in newly-diagnosed AML patients age \geq 60 years.

2.2.2 To evaluate the feasibility of consolidation with reduced-intensity conditioning and allogeneic hematopoietic stem cell transplantation from HLA-identical donors in patients who achieve a response to induction therapy, including the incidence of successful engraftment, acute and chronic graft-versus-host disease, transplant-related mortality, and its impact on overall survival in comparison to patients receiving chemotherapy.

2.2.3 To evaluate the duration of remission and disease-free survival of patients in complete remission following completion of consolidation therapy who are subsequently randomized to receive scheduled low-dose decitabine maintenance in comparison with observation.

2.2.4 To perform expression and methylation profiling on all patients receiving decitabine and to correlate their integrated epigenetic signatures with response to decitabine.

2.2.5 To examine the epigenetic profiles of remission marrow in patients randomized to observation vs. decitabine to determine whether epigenetic signature of apparently morphologically normal bone marrow is predictive of relapse or response to decitabine maintenance.

2.2.6 To explore the possible association of response to clofarabine with ABC-transporter P-glycoprotein (Pgp).

2.2.7 To assess the intensity of expression of CXCR4 on diagnostic leukemia cells and to correlate this parameter with other established prognostic factors

2.2.8 To assess the entire spectrum of somatic mutations and affected pathways at diagnosis of AML and elucidate the association between gene mutation and outcome.

2.2.9 To examine the impact of smoking, obesity, regular acetaminophen use, regular aspirin use, benzene exposure, living in a rural/farm environment and some other underlying exposures and lifestyle factors associated with AML development on OS.

Rev. 2/13

Rev. 2/12

Rev. 2/12

Rev. 2/13

Rev. 2/13

2.2.10 To investigate potential correlative results between array CGH findings and acute myeloid leukemia patient characteristics.

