The induction CR rates will be monitored to allow for early stopping in favor of inferiority using the repeated confidence interval methodology described by Jennison and Turnbull (123). Interim analyses will be conducted for induction CR rates when induction response data is available on 25%, 45%, 65%, 85% and 100% of patients. At each interim analysis, the two-sided 95% repeated confidence interval on the difference of CR rate (CR rate of standard treatment – CR rate of clofarabine) will be computed. This repeated confidence interval uses the critical value from a truncated O'Brien-Fleming error spending rate function with an overall one-sided 2.5% error rate. If the confidence interval lies entirely above 0, the induction randomization may need to be stopped due to the inferiority of clofarabine and subsequent patients will directly be assigned to standard treatment arm.

Another objective of this trial is to determine the effect of decitabine on disease free survival (DFS) as a maintenance therapy in comparison with observation. DFS is defined as the time from the second randomization to relapse or death without relapse. If 25% of patients who do not receive allogeneic transplant go through the second randomization, there will be 172 patients = randomized to either the decitabine arm or the observation arm.

We assume that the long-term cure rate for the observation arm is 10% and the median DFS in the non-cured group is 7 months. The study will have 90% power to detect approximately a 36% reduction in the DFS hazard rate in the decitabine maintenance therapy arm. This power calculation is based on a one-sided log-rank test at the significance level of 0.1 and assumes 5 years of accrual and 2 years of follow-up after the completion of the accrual. The number of DFS events needed is 140. The primary analysis of DFS will be an intention-to-treat analysis and will use a one-sided log rank test stratified on the induction and consolidation therapy and on patient age and cytogenetics.

Another secondary objective of this study is to evaluate the impact of consolidation with non-ablative conditioning and allogeneic hematopoietic stem cell transplantation with an HLA-identical sibling on overall survival in patients who achieve a 'morphologic leukemia-free state'.

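### Epigenetic and expression features are chosen on relapse and then related to DFS, apparently in the same patients and with no signature-by-arm term, so the association is strongly biased and the decitabine-response part of objective 2.2.5 is not tested

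*Combined protocol and SAP*

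**What the plan says.** Objective 2.2.5 (section 2.2) asks whether the epigenetic signature of remission marrow "is predictive of relapse or response to decitabine maintenance". Objective 2.2.4 asks for signatures in patients receiving decitabine to be correlated with response to it.

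Section 9.8 carries these out in two steps.

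- **Selection.** A referenced method is used to "identify epigenetics signatures which are different between patients who relapsed and patients who did not relapse". For expression: "Supervised analyses will be used to identify genes that are differentially expressed between patients who relapsed and patients who did not relapsed".
- **Association.** "Signatures identified by epigenetic analysis will be correlated with DFS using a LARS/LASSO approach", and this is done separately in each maintenance arm. A closing sentence repeats the LARS/LASSO step for genes and epigenetic signatures without naming an arm.

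Section 9.4 defines the outcome: "DFS is defined as the time from the second randomization to relapse or death without relapse".

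On numbers, section 9.8 says: "Assume that 86 patients will receive decitabine maintenance treatment and 86 patients will be randomized to the observation arm", with 45% to 50% of them having usable material. It calls these analyses exploratory. For these signatures it names no hold-out set, nested cross-validation, permutation test or treatment interaction. Later in the same section, the mutation analysis has resampling-based multiplicity control and treatment-by-mutation interaction tests. Its risk-group models have a 423/212 training and validation split.

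**The concern.** There are two separate problems.

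1. **Circularity.** Features are kept because they separate relapsers from non-relapsers. They are then related to an outcome that relapse largely determines, in what appear to be the same patients. With thousands of features and about 40 patients per arm, pure noise will look associated with DFS far more often than the nominal rate.

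2. **Prognostic versus predictive.** A signature can be associated with DFS in the decitabine arm simply because it marks worse disease. To say that it predicts response to decitabine, its association with DFS must differ between decitabine and observation. Separate fits in each arm do not estimate or test that difference.

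At stake is whether these secondary analyses can be interpreted. Sections 1.6.3.1 and 10.3.1 intend the epigenetic data collected at enrollment to inform the design of later group trials.

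**Working it through.** **Inputs from the documents**

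- 747 patients, 8% transplanted, 25% of the rest entering the second randomization (sections 9.1, 9.2, 9.4).
- 45% to 50% with usable material (section 9.8).
- Observation-arm DFS: 10% cured, 7-month median in the non-cured, 5 years of accrual plus 2 of follow-up (section 9.4).
- 140 DFS events in the original design (section 9.4); 125 events among 172 patients after redesign (section 9.5).

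**Reproducing the plan's figures**

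- Maintenance patients: 747 × 0.92 × 0.25 = 171.8, so 172, or 86 per arm. This agrees.
- DFS events for hazard ratio 0.64, one-sided 0.1, 90% power: Freedman gives 137 and Schoenfeld 132, against the stated 140. Under the stated cure model, with follow-up uniform from 24 to 84 months, 140.8 events are expected. The plan's figure is sound.
- Profiled patients: 0.45 × 86 = 38.7 and 0.50 × 86 = 43 per arm, so 77 to 86 in total.

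The plan gives no operating characteristics for the signature analysis, so there is nothing further to reproduce.

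**Bias when no feature is related to outcome**

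Assumptions not in the documents: independent noise features, 50 carried forward after a t-test, and DFS event status standing in for relapse status.

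*Selection followed by Cox LASSO with 5-fold cross-validation on DFS in one arm.* There were 39 or 43 patients, a non-event share of 10% or 27% (27% from 1 − 125/172), and about 200 runs per setting. Share of runs with p<0.05:

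| Procedure | 1,000 features | 20,000 features |
|---|---|---|
| Selection pooled over arms, same patients | 66%–82% | 81%–98% |
| Selection within arm, same patients | 79%–88% | 93%–100% |
| LASSO on 50 unselected features | 30%–38% | 29%–35% |
| Selection and fit on two thirds, test on one third | 2.5%–5.7% | 1.5%–6.3% |

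The LASSO's own cross-validation does not remove the bias, because selection sits outside it.

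*Simpler pipeline.* 40 patients, 5,000 features, signed-sum score split at its median, log-rank test:

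| Setting | p<0.05 |
|---|---|
| Plan's follow-up (24–84 months), 10% cured | 49% |
| Fixed 24 months, 10% cured | 77% |
| 25% non-events | 96% |

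A repeat with 400 data sets per setting gave 43%, 80% and 97%. The low end of the overall range is therefore about 45%. With selection moved inside 5-fold cross-validation, a plain log-rank test on the cross-validated scores still rejected in 8% to 15% of null data sets.

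**What a signature-by-arm test could detect**

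For a signature with 50% prevalence and equal arms, the standard error of the log ratio of hazard ratios is 4/√E.

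- Events among profiled patients: 77.4 × 125/172 = 56, up to 86 × 140/172 = 70.
- Detectable ratio, 80% power, two-sided 0.05: exp(2.80 × 4/√56) = 4.5 and exp(2.80 × 4/√70) = 3.8.
- At one-sided 0.1: exp(2.12 × 4/√56) = 3.1 and exp(2.12 × 4/√70) = 2.8.
- Power for a ratio of 2, two-sided 0.05: 25% to 30%.

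**The case against.** The strongest reply is that the work is declared exploratory and sets no p-value threshold for these signatures, so there is no false-positive rate to inflate. That lowers the status of any claim. It does not make a correlation informative when noise produces it about half the time or more.

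Several narrower points stand:

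- The feature counts and the top-50 rule are assumptions, and the rate moves a good deal with follow-up and non-event share. A reader might infer that a false association is nearly guaranteed. The runs support that only for array-scale feature counts or a larger non-event share.
- Not all the inflation comes from selection on relapse: LASSO on 50 unselected features already gave 29% to 38%.
- Use of the same patients for both steps is inferred, because no second set is named. The explicit arm-by-arm wording covers the epigenetic sentence, not the closing gene-expression one. Selection itself may pool the arms.
- The error control of the referenced selection method cannot be judged from the documents. Section 10.4.2 mentions multiple-testing correction and machine-learning epigenetic classifiers, but no nested validation for this analysis.
- A reader might infer that response to decitabine is never examined. That is too broad. Objective 2.2.4 is a correlation within decitabine patients and needs no interaction, and the relapse half of 2.2.5 can be studied within arms. Only the decitabine-response half of 2.2.5 needs a between-arm contrast.
- The statement about guiding future trials follows the text on signatures captured at enrollment. The remission-marrow aim (sections 1.6.3.2 and 10.3.2) carries no such statement.

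**Conclusion.** The concern holds in this form. Following the sequence in section 9.8, choosing features on relapse and then relating them to DFS in the one profiled pool it names, gives a strongly biased association. Under the null, about 45% to 100% of data sets reach p<0.05. This rests on the assumed 1,000 to 20,000 independent features with 50 carried forward, on DFS event status as a proxy for relapse, and on the same patients serving both steps. Many deaths without relapse would weaken the link between selection and outcome.

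The second part rests on the text alone. With separate arm fits and no signature-by-arm term, the plan does not test whether a signature predicts response to decitabine rather than prognosis, which is the decitabine-response half of objective 2.2.5. The primary endpoint and the randomized maintenance comparison are unaffected. The change should be made because the remedy is cheap and section 9.8 already uses comparable safeguards for mutations.

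**What to change.** Amend section 9.8 as follows.

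1. Run feature selection and the LASSO fit together inside each cross-validation fold, for methylation and expression alike, and report the cross-validated association with DFS. With 10% non-events, an arm of 40 has about four non-relapsers, so folds should be stratified by relapse status.
2. Take any p-value from permuting the whole pipeline, since a log-rank test on cross-validated scores remains somewhat above nominal.
3. For the decitabine-response question in 2.2.5, fit one Cox model for DFS across both maintenance arms with arm, cross-validated signature score and their interaction. Report the interaction estimate with its confidence interval.
4. State the low interaction power beside it: a detectable ratio of hazard ratios of about 3.8 to 4.5 at 80% power, two-sided 0.05. If the study does not reopen under section 9.5, the 120 randomized patients give only about 54 to 60 profiled (120 × 0.45 to 120 × 0.50), and power falls further.

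The cost is more computation and weaker apparent associations. No new samples are needed.

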10.4.2 Methodology

Samples from E2906 will be analyzed as patients are accrued to the trial. High quality genomic DNA will be extracted from mononuclear cells provided by the LTSL, as done previously for E1900 and E3999 specimens. Control DNA will be isolated from normal T-cell contaminating the leukemia specimens or from remission samples. Genomic DNA from blasts and control cells will be subjected to Agilent SureSelect sequence capture followed by bar-coding and sequencing on our HiSeq2000. Genomic DNA will also be processed for reduced representation bisulfate sequencing and examined on the HiSeq2000. Excess DNA will be stored and made available to ECOG-ACRIN for distribution to other approved investigators. Validation will be done using amplicon based sequencing on our existing resequencing platform (used for E1900 and E3999 mutational studies) to facilitate higher throughput candidate gene mutational analysis of genomic DNA. Wherever possible, mutations will be analyzed in remission or T-cell DNA to ascertain whether specific alterations are somatic or in the germline. We will use our suite of computational biostatistical tools for identifying candidate somatic mutations. The data set will be evaluated for genetic signatures that distinguish

patient subtypes using unsupervised methods such as hierarchical clustering, principal component analysis, and consensus clustering. Signatures of co-occurring lesions will be determined using supervised methods including moderated T tests with correction for multiple testing, LEMMA, random forest, etc. The biological connectivity between gene sets and their genomic features will be derived using tools including iPAGE, FIRE, IPA, etc. We will use a series of statistical approaches to determine whether lesions in specific recurrently affected genes or pathways indicate risk of chemotherapy failure, disease recurrence or survival. In addition to univariate and multivariate analyses, we will use machine-learning algorithms like SuperPC and BDVAL to identify genetic, epigenetic, and integrated classifiers. All mutations detected will be validated by repeat PCR and sequencing on the unamplified diagnostic sample. Wherever possible, matched control DNA (remission or T-lymphocyte DNA) will be resequenced to determine if candidate disease alleles are somatic or present in germline.

Rev. 2/12 10.5 AML Prognostic Factors & Mechanisms of Resistance

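### Section 9.8 screens genes and methylation signatures by relapsed versus not relapsed, which does not match the DFS endpoint of the next step and usually costs power

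*Combined protocol and SAP*

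**What the plan says.** Section 9.8 describes two platforms with the same two steps.

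- Methylation: the methods of a cited pipeline paper are used to "identify epigenetics signatures which are different between patients who relapsed and patients who did not relapse".
- Expression: after filtering and clustering, "Supervised analyses will be used to identify genes that are differentially expressed between patients who relapsed and patients who did not relapsed". The test is not named.
- Second step: "Genes or epigenetic signatures identified by gene expression or epigenetic analysis will be correlated with DFS using LARS/LASSO approach". For methylation this is done separately in each maintenance arm.

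On size, "Assume that 86 patients will receive decitabine maintenance treatment and 86 patients will be randomized to the observation arm", and 45% to 50% of them are expected to have usable material. On status, "These analyses will be exploratory in nature". No significance level, effect size or power is given for the screen.

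Section 9.4 measures DFS from the second randomisation to relapse, or to death without relapse. It adds: "We assume that the long-term cure rate for the observation arm is 10% and the median DFS in the non-cured group is 7 months". Section 9.8 does not say where the screen puts deaths in remission or patients censored early.

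**The concern.** The two steps use different outcomes. The second uses time and counts death in remission as an event. The first uses neither time nor censoring, so a relapse at 2 months counts the same as one at 40 months. Taken at its words, the group that did not relapse holds long-term survivors, patients who died in remission and patients not yet followed for long. A feature linked to early failure can then look weaker than it is.

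What is at stake is objectives 2.2.4 and 2.2.5, the epigenetic questions attached to the maintenance randomisation. At most about 86 patients will be profiled, and a feature missed by the supervised contrast may not be carried into the DFS model.

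**Working it through.** **Inputs from the documents**
- Profiled patients: 172 × 0.45 = 77 to 172 × 0.50 = 86 pooled, or 39 to 43 per arm. If the trial closes at 120 randomised: 54 to 60.
- DFS model (9.4): 10% cured, median 7 months in the rest, 5 years of accrual plus 2 of follow-up, hazard ratio 0.64, one-sided alpha 0.1, 90% power, 140 events.
- Section 9.5: 125 events in 172 patients (73%) if reopened; 90 events in 120 patients (75%) if closed.

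**The plan's own figures.** The screen has no stated power, so the nearest figures are those for DFS. Freedman's formula gives [(1 + 0.64)/(1 − 0.64)]² × (1.2816 + 1.2816)² = 137 events, against 140 stated. With 140 events, z = (√140/2) × |ln 0.64| − 1.2816 = 1.36, or 91% power. Simulating the cure model gives 140.8 events in 172. For Section 9.5, 125 events at hazard ratio 0.63 give 90.3%, and 90 events at 0.64 with alpha 0.15 give 86.0%. All agree with the plan.

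**How many patients are event-free**
- Observation curve alone, follow-up uniform on 24 to 84 months: 0.1 + 0.9 × [2^(−24/7) − 2^(−84/7)]/(60 × ln 2/7) = 0.1 + 0.9 × 0.0156 = 0.114, or 9.8 of 86. With a marker effect of 0.4 per SD this rises to about 11.5.
- The plan's 140 events: (172 − 140)/172 = 18.6%, or 16 of 86.
- Section 9.5: (172 − 125)/172 = 27.3%, or 21 of 77 and 23.5 of 86. With a marker effect the simulations give 21 to 25.

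**Power of the two screens.** Assumptions not in the documents: one standard-normal feature, log-hazard 0.4 to 0.5 per SD (or hazard ratio 1.5 to 2.0 per SD), and two-sided per-feature thresholds from 0.05 to 0.001. The Cox score test is Z = U/√V. U sums, over events, the feature value minus its risk-set mean; V sums the risk-set variances. The comparator is a two-sample t-test by relapse status. With no effect, the two rejected 5.8% and 5.1% at the 5% level. Results for 86 patients and no deaths in remission:

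| Setting | Cox vs binary, p<0.05 | Cox vs binary, p<0.001 |
|---|---|---|
| Original model, 0.4 per SD | 91% vs 74% (17 points) | 48% vs 21% (27) |
| Original model, 0.5 per SD | 98% vs 89% (9) | 77% vs 41% (36) |
| Original model, arms mixed at 0.64, HR 1.5 per SD | 89% vs 76% (13) | 42% vs 23% (19) |
| Event share of 9.5, HR 1.5 per SD | 87% vs 80% (7) | 40% vs 28% (12) |
| Event share of 9.5, HR 1.75 per SD | 99% vs 96% (3) | 81% vs 63% (18) |
| Feature acts on cure only, log-odds 1.0 per SD | 60% vs 76% (−16) | 14% vs 27% (−13) |

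The event share of 9.5 was approximated by setting the cured fraction to 25%. Over 54 to 86 patients and HR 1.5 to 2.0 per SD, the loss there runs from 1 point (100% vs 99%; 86 patients, HR 2.0, p<0.05) to 22 points (73% vs 51%; 54 patients, HR 2.0, p<0.001).

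**Deaths in remission.** Suppose they make up 10% of DFS events (assumed), with 86 patients, the 9.5 event share, HR 1.5 per SD and p<0.05. If these deaths share the feature's effect, power is 88% (Cox on DFS), 84% (Cox on relapse) and 65% (binary). If they are unrelated to it, power is 80%, 85% and 75%. Either Cox screen beats the literal yes/no grouping; which Cox outcome is better depends on what the deaths reflect.

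**The case against.** The strongest objection concerns the model. The loss is computed with features acting proportionally on the hazard, which is what a Cox score test is built for. The plan's own DFS model is a cure mixture. If a feature only changes who is cured, the yes/no contrast does better, as the last table row shows. This stands, and it is the reason to keep the contrast as a sensitivity analysis.

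The second objection is that the stated aim includes predicting relapse, and relapse status speaks to that biology, whereas DFS mixes in non-leukaemic deaths. This also stands, but it argues for cause-specific relapse time, not for dropping time.

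Third, a pooled main-effect screen could dilute features that act in one arm only, yet response to decitabine is a goal and the methylation step runs by arm. This stands and shapes the fix.

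Some stronger readings are tempting but not supported.
- A reader might infer that only 11 or 12 patients are relapse-free. That holds for the observation curve alone; the events in 9.5 imply about 21 to 25.
- A reader might infer that the plan decides to count remission deaths as good outcomes. Section 9.8 leaves the group undefined, so this is only its literal meaning.
- A reader might infer that a feature failing the screen is lost for good. Section 9.8 also lists clustering for expression, and Section 10.4.2 says that "we will use machine-learning algorithms like SuperPC and BDVAL" for further classifiers, so other routes may exist.
- The t-test comparator is an assumption, since the expression test is unnamed and the methylation method is in a source not available here.

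**Conclusion.** The mismatch is real: the screen ignores time and follow-up, and its wording conflicts with the DFS definition used in the next step. Under proportional effects the cost is about 9 to 36 points of power for 86 patients under the original DFS model (0.4 to 0.5 per SD, thresholds 0.05 to 0.001). At the event share of Section 9.5 it is roughly 1 to 22 points (HR 1.5 to 2.0 per SD, 54 to 86 patients). Both ranges exclude deaths in remission and rest on effect sizes and thresholds that the plan does not give. The sign can reverse for features acting only on cure.

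A reader might infer that a fixed loss is built into the plan, or that a power statement is wrong. Neither follows. The analysis is labelled exploratory, no power is claimed for it, and the trial's treatment comparisons are untouched. This is a worthwhile improvement in efficiency and consistency.

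**What to change.** In Section 9.8, for both expression and methylation:

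- Make the primary screen a per-feature Cox score test on DFS from the second randomisation. If relapse biology is the target, use cause-specific relapse instead, censoring deaths in remission. State which is chosen.
- For prognostic features, stratify the test by maintenance arm. For response to decitabine, run it within arm or test a feature-by-arm term.
- Carry the selected features to the LARS/LASSO step as now planned.
- Keep relapsed versus not relapsed as a sensitivity analysis, and do not count deaths in remission or patients with short follow-up as non-relapsers.

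The cost is SAP wording, analysis code and a little more analysis work. DFS times are already collected for the maintenance comparison. Some sensitivity is given up for features acting only on cure, which the retained contrast covers.
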